- The Department of Health and Human Services, Office of Human Research Protections, and other governmental agencies and regulatory agencies;
- Other researchers when a review board approves the sharing of the health information.
- Others, if the law requires.

Data in non-identifiable form will be available, upon request to reanalyze the data, to qualified researchers. However, again, no identifying information will be provided. Data kept in identifiable form (recordings) will be destroyed after the records retention period required by state and/or federal law.

30. Ancillary and post-trial care

Provisions, if any, for ancillary and post-trial care, and for compensation to those who suffer harm from trial participation

N/A

31. Dissemination policy

31a. Plans for investigators and sponsor to communicate trial results

To participants, healthcare professionals, the public, and other relevant groups (eg, via publication, reporting in results databases, or other data sharing arrangements), including any publication restrictions

Results will be presented in peer-reviewed journal articles (with appropriate deposit in publicly-accessible databases as required as a condition of NIH funding), conference presentations, and community presentations.

31b. Authorship eligibility guidelines and any intended use of professional writers

The research team will adhere to the American Psychological Association's (2001) publication credit guidelines for authors (p. 350-351; Principle 6.23, a-c).

Authorship order is based on scientific contributions to the research and the manuscript. Proposed authorship order is subject to renegotiation if an author fails to fulfill his/her agreed upon role in a timely manner. If the manuscript has not progressed within 6 months of the date of this agreement, the data return to the authorship pool and another author may be designated to take the lead on the paper.

31c. Plans, if any, for granting public access to the full protocol, participant-level dataset, and statistical code

N/A

32. Appendices

- Study consent form (next page)

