- (H3) completion rates for daily activities will be similar to previous web-based interventions.

Aim 4 (Assess the impact of the intervention on learning and symptoms)

- (H4) participants will show significant learning as evidenced by increases in correct responses to knowledge questions from baseline to post
- (H5) participants in the intervention condition will evidence less high-risk drinking and PTSD at 3-month follow-up than participants in the assessment-only condition.

8. Description of trial design

Type of trial

(eg, parallel group, crossover, factorial, single group)

Parallel group, two arm

Allocation ratio

1:1

Framework

(eg, superiority, equivalence, noninferiority, exploratory)

Superiority

Methods: Participants, Interventions, and Outcomes

9. Study setting

Description of study settings

Although the intervention will be conducted online, participants will be recruited from the Seattle–Tacoma–Bellevue, WA Metropolitan Statistical Area (defined by the US Census Bureau). According to the [2018 American Community Survey](#), this represents 3,939,363 people. The median age of the population in this area is 37, and the population is 50% female. The population is 62% White, 14% Asian, 10% Hispanic, 6% Black, 6% two or more races/ethnicities, and 2% other. The median per-capita income is \$46,204, and the median household income is \$87,910. The majority of individuals in this area (92.9%) are high-school graduates, and 43.6% have a bachelor's degree or higher.

Reference to where list of study sites can be obtained

N/A

10. Eligibility Criteria

Inclusion criteria

- Informed consent
- Self-identification as female
- Sexual assault, defined as endorsement of unwanted, attempted or completed sexual contact in the past 10 weeks on the Sexual Experiences Survey- Revised
- Age ≥ 18
- English fluency
- Telephone and internet access for 3 months
- Consumption of ≥ 1 alcoholic drink in the past month
- ≥ 1 episode of high-risk drinking in past 6 months, defined as either more than 3 drinks on a given day or more than 7 drinks in a given week
- At least 3 symptom clusters endorsed on the PTSD Checklist

Inclusion criterion	How assessed at phone screening	How confirmed at baseline
Informed consent	Verbal consent	Electronic consent
Self-identification as female	Single item	N/A
Age ≥ 18	Single item	N/A
Past-10-week sexual assault history	
• “Have you experienced unwanted sexual	N/A

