	
contact?”
 
 “On what date or around what date did you last experience this?” “Did the recent assault involve...” 
 Completed penetration? Attempted penetration? Unwanted sexual touching? If the participant answers no to all, ask “How would you describe the unwanted sexual experience?” 	
Telephone and internet access for 3 months	Single item	N/A
English fluency	Single item	N/A
Consumption of ≥ 1 alcoholic drink in the past month	In the past month, how many days did you drink alcohol?	Quantity Frequency Questionnaire
≥ 1 episode of high-risk drinking in past 6 months, defined as either more than 3 drinks on a given day or more than 7 drinks in a given week	
“In the past 6 months, what is the greatest number of drinks you had on a single day? By “drink” we mean a 12 ounce can or glass of beer or cooler, a 5 ounce glass of wine, or a drink containing 1 shot of liquor.”
 
“In the past 6 months, what is the greatest number of drinks you had in a single week?”
	N/A

At least 3 symptom clusters endorsed on the PTSD Checklist	Primary Care PTSD Screen assessed in relation to the recent unwanted sexual experience (score of 2 or more)	On the PTSD Checklist (assessed in relation to the recent unwanted sexual experience), at least 3 of the following criteria met (based on responses of “moderately” or greater): 1 B item (questions 1-5), 1 C item (questions 6-7), 2 D items (questions 8-14), 2 E items (questions 15-20)
--	---	---

Exclusion criteria

- Active suicidality as assessed by the Ask Suicide Screening Questionnaire
- Psychosis as assessed by The Psychosis Screener

11. Interventions

11a. Interventions for each group with sufficient detail to allow replication, including how and when they will be administered

Intervention

The intervention is a phone app (“THRIVE”) intended to be used daily for 3 weeks, beginning within 10 weeks of a sexual assault.

Participants will first complete an onboarding process that orients them to the app, the daily surveys, and the tasks and activities that they will be asked to complete daily. They will then complete two onboarding activities: one for the behavioral activation component (in which they generate an initial list of self-care activities), and one for the cognitive restructuring component (in which they learn about stuck points).

The dashboard of the app will contain:

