- A banner indicating the consecutive days that participants have completed activities
- A link to an **activity involving behavioral activation** emphasizing engagement with alcohol-free social activities, which they will complete daily
- A link to **activity involving cognitive restructuring** skills with an emphasis on mitigating the harm of cognitive distortions arising from negative social reactions and other social factors, which they will complete daily
- A link to **relationship-targeted activities** that complement the

behavioral activation and cognitive restructuring skills, which will be completed as needed

- A link to a survey, which they will complete daily
- A link to a “mood tracker” that charts responses to daily surveys
- A link to resources

Coach

- The coach will check in weekly by phone or Zoom and will do the following:
 - Check on mood
 - Troubleshoot activity completion (e.g., help participants learn how to address a difficult stuck point)
 - Assist with issues related to use of the app itself (e.g., technical issues, glitches)
 - Provide resources as needed
 - Monitor and encourage intervention engagement

Comparison

Participants will first complete an onboarding process that orients them to the app and the daily surveys.

The dashboard of the app will contain:

- A banner indicating the consecutive days that participants have completed their survey
- A link to their survey, which they will complete daily
- A link to a “mood tracker” that charts responses to daily surveys
- A link to resources

Coach

- The coach will check in weekly by phone and/or Zoom and will do the following:
 - Check on mood
 - Assist with issues related to use of the app itself (e.g., technical issues, glitches)
 - Provide resources as needed

11b. Criteria for discontinuing or modifying allocated interventions for a given trial participant

Participants who withdraw consent for participation should no longer be contacted by study staff or sent automated reminders to complete study tasks.

11c. Strategies to improve adherence to intervention protocols, and any procedures for monitoring adherence

The phone screener will:

- Discuss the process of randomization to a condition with the participant.

- Emphasize that the app will be offered at the end of the baseline survey, so they must finish the survey to access the app.

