Given evidence that human contact increases adherence to app interventions, we will provide participants in both conditions with ongoing phone coaching. All screened participants, regardless of randomization or condition, will get one phone or Zoom call from a coach to ensure that app installation and onboarding were successful (if randomized), answer questions (for all participants), encourage adherence to surveys (if randomized), and provide resources (if not randomized). This call will be scheduled during the phone screening and will occur within 3 business days of screening. The coach will be informed of the individual's condition before the call.

Participants in both conditions will be offered three additional weekly phone/text/Zoom check-ins with their coach to troubleshoot progress and skill application (intervention condition only), check in on overall well-being (both conditions), encourage daily survey completion (both conditions), monitor risk (both conditions), and troubleshoot technical difficulties (both conditions). Coaches will be able to access participant data (e.g., activity data, time spent in the app, self-report data) prior to the weekly appointment.

[figure not shown]
11d. Relevant concomitant care and interventions that are permitted or prohibited during the trial

Participants will not be restricted from accessing any care or interventions during the course of the trial. It is likely that individuals recruited from the Harborview Center for Sexual Assault and Traumatic Stress (a primary recruitment site) will receive treatment for sexual-assault-related distress while enrolled in the study.

12. Outcomes

See ClinicalTrials.gov.

13. Participant timeline

14. Sample size

Estimated number of participants needed to achieve study objectives

$n = 20$ in intervention condition; $n = 20$ in control condition

How sample size was determined

Including clinical and statistical assumptions supporting any sample size calculations

The study was designed to collect information about feasibility; thus, the sample size was set for practical reasons rather than detecting effect sizes or significance testing. A control group was included to obtain pilot estimates of effect sizes, and we will have

statistical power of 0.80 to detect an effect size of count ratio of 1.40, based on a mean base rate RAPI drinking problems count of 6 in untreated women from a preliminary study (R21AA016211 PI: [name]).

15. Recruitment

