
18b. Plans to promote participant retention and complete follow-up

List of any outcome data to be collected for participants who discontinue or deviate from intervention protocols

The following steps will be taken to promote retention:

- We will collect extensive contact data from participants and attempt to reach them for all follow-up assessments unless directed otherwise.
- The daily surveys will be accessed from within the app, which is intended to increase the likelihood that participants complete both surveys and activities
- Participants can opt in to receive a text from the app prompting them to complete a survey.
- Participants will be paired with a coach, who will remind them to complete baseline and post-intervention surveys
- Participants will receive reminders from study staff to complete the baseline, post-intervention, and 3 month surveys.
- Participants will be paid \$3 per day of survey completion (daily participation will be incentivized to make daily data analysis possible) and \$10 bonus for completion of 7 consecutive days. Participants will be paid \$20, \$40, and \$60 for participation in each assessment (at baseline, termination, and 6 3 months post-termination), respectively. Total possible remuneration will be \$213 for both conditions. Participants will be paid for each survey and assessment they complete, even if they do not complete all assessments.
- The screener will emphasize the importance of completing both daily surveys and daily intervention tasks if assigned to the intervention.
- The screener will instruct participants to complete the baseline survey once they terminate the phone call.

19. Data management

Plans for data entry, coding, security, and storage

Including any related processes to promote data quality (eg, double data entry; range checks for data values). Reference to where details of data management procedures can be found, if not in the protocol.

Entry and coding

Data will be completely digital; no data entry will be needed. In some cases, scale scores will be automatically calculated by custom programming. When this does not occur, the first author will create SPSS syntax and a data dictionary referencing scoring procedures.

Security and storage

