All data will be identified only by a Personalized Identification Number (PIN). Data will be collected using a secure server. Electronic protection is provided by a commercial-grade firewall, with continuous monitoring of the server for any attempts at electronic invasion. The password to the account will only be known to the Principal Investigator, Mentors, and other relevant research staff. All data stored in the online repository will be encrypted. A master list of names and PINs will be stored in a password-protected database under the supervision of the Principal Investigator, and will be available only to research staff on this project. Research assistants will receive training that includes emphasis upon the importance of confidentiality of information, and all personnel on the project (including graduate and undergraduate research assistants and study staff) will complete the required NIH training in protection of human research participants. All staff will sign confidentiality statements. Data will be retained on computers with restricted and password protected access, without links to the master code list. All data based on this research will be reported in aggregate form. No individual respondents will be identified.

The link between identifiers and the research data will be destroyed after the records retention period required by state and/or federal law.

20. Statistical methods

20a. Statistical methods for analyzing primary and secondary outcomes

Reference to where other details of the statistical analysis plan can be found, if not in the protocol

Relevant to Aim 3 (Assess participant reaction to the intervention), the hypothesis that most participants will respond positively on items assessing satisfaction with the intervention (H1) will be assessed via descriptive statistics, visualizations, and multilevel models; 95% CIs will determine whether satisfaction ratings are significantly better than “neutral.” The hypothesis that participants will report above-average usability on a standardized measure (H2) will be assessed via mean scores on the System Usability Scale; 95% CIs will determine whether usability ratings are significantly different from a score of 68/100 (indicating above-average usability). The hypothesis that completion rates for daily activities will be similar to previous

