web-based interventions (H3) will be tested via descriptive statistics, visualizations, and multilevel models; 95% CIs will determine whether the number of days completed is significantly different from 10 and the percent of days completed is significantly different from 71.43%.

Relevant to Aim 4 (Assess the impact of the intervention on learning and symptoms), as this study was not powered to detect all effects of interest, we rely primarily on the direction and magnitude of effect sizes to interpret results and conduct significance tests in an exploratory manner. The hypothesis that participants will show significant learning as evidenced by increases in correct responses to knowledge questions from baseline to post (H4) will be tested via paired-samples t-tests. The hypothesis that participants in the intervention condition will evidence less high-risk drinking and PTSD at 3-month follow-up than participants in the assessment-only condition (H5) will be tested via mixed-effects models. Because they are non-negative discrete integers that typically show a positive skew, Poisson or negative binomial distributions will be examined. Dummy variables for the intervention condition with the control as the reference will be included. We will examine time by condition interactions to assess effects at each follow-up.

20b. Methods for any additional analyses

(eg, subgroup and adjusted analyses)

We may include additional covariates to increase precision or if there is evidence that randomization did not adequately balance covariate distributions by condition.

20c. Analysis population and missing data

Definition of analysis population related to nonadherence (eg, as randomized analysis), and any statistical methods to handle missing data (eg, multiple imputation)

We will use an intent to treat analysis, in which participants will be retained in the group to which they were originally randomized. Outcome data from all participants will be included in analyses. We will also explore the use of randomization-based efficacy estimators (White, 2005). We will use maximum likelihood estimation for missing data.

Methods: Monitoring

21. Data monitoring

21a. Data monitoring committee

Composition of data monitoring committee (DMC)

N/A

Summary of its role and reporting structure

N/A

Statement of whether it is independent from the sponsor and competing interests

Reference to where further details about its charter can be found, if not in the protocol

N/A

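### H3 is judged against both 10 days and 71.43% of days, which agree only on a 14-day programme; the app runs 21 days, no rule reads a split result, and a test for difference cannot show similarity

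*Combined protocol and SAP*

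**What the plan says.** Section 7 states H3 as a prediction that "completion rates for daily activities will be similar to previous web-based interventions". Section 20a repeats the hypothesis and adds the decision rule: descriptive statistics, visualizations and multilevel models, with 95% confidence intervals on whether "the number of days completed is significantly different from 10 and the percent of days completed is significantly different from 71.43" percent. It gives no source for either figure, no denominator for the percent of days, and no order of priority between the two tests.

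Section 11a describes the app as "intended to be used daily for 3 weeks". Its list of dashboard items has a behavioral activation activity "emphasizing engagement with alcohol-free social activities, which they will complete daily", and a cognitive restructuring activity on the same daily schedule. Section 18b sets the maximum payment at $213 for both arms and notes that "The daily surveys will be accessed from within the app". Section 12 gives no outcome definitions, only "See ClinicalTrials.gov".

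**The concern.** The two benchmarks sit side by side as if they were one target on two scales. They are one target only for a 14-day programme. If each participant is offered 21 days, count and percent are the same variable rescaled, so the two null values cannot both be true, and completion close to one benchmark will tend to be declared different from the other. The plan would then have to say whether H3 is supported, and it has no rule for that.

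There is a second difficulty in the same sentence. H3 predicts similarity, but the rule looks for a difference. With 20 participants, completion well below the benchmark could be non-significant and then be reported as similar.

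Completion is a central result of a feasibility study, so its criterion should be readable in only one way.

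**Working it through.** **Inputs from the documents.** Benchmarks of 10 days and 71.43% (20a); daily use for 3 weeks, i.e. 21 days (11a); payments of $3 per daily survey, $10 per 7 consecutive days, and $20, $40 and $60 for the three assessments, maximum $213 (18b); 20 participants in the intervention arm (14).

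**Step 1: reproduce the plan's figure.** 10/14 = 0.7143. Fourteen is the only whole number of days on which 10 days gives 71.43%.

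**Step 2: check the programme length.** Assessments: 20 + 40 + 60 = 120.
- 21 days: 120 + 21 × 3 + 3 × 10 = 213, the stated maximum.
- 14 days: 120 + 14 × 3 + 2 × 10 = 182.

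The payment is for surveys rather than activities, but both sit in the same app, and the total agrees with the 3 weeks in 11a.

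**Step 3: put the benchmarks on 21 days.** 10/21 = 47.6%; 15/21 = 71.43%. The gap is 5 days, or 5/21 = 23.8 percentage points.

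**Step 4: when do the two tests disagree?** Assumptions: a one-sample t-interval on days completed, n = 20, all 21 days as denominator. Half-width = t(0.975, 19)/√20 × SD = 2.093/4.472 × SD = 0.468 × SD. The documents give no SD, so a range is shown; 6.34 is the SD of an even spread over 0 to 21 days, √((22² − 1)/12).

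| SD (days) | Half-width | Means not different from 10 | Means not different from 15 | Means not different from either |
|---|---|---|---|---|
| 4 | 1.87 | 8.13–11.87 | 13.13–16.87 | none |
| 5 | 2.34 | 7.66–12.34 | 12.66–17.34 | none |
| 6.34 | 2.97 | 7.03–12.97 | 12.03–17.97 | 12.03–12.97 |
| 8 | 3.74 | 6.26–13.74 | 11.26–18.74 | 11.26–13.74 |

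One interval can cover both benchmarks only if its half-width is at least 2.5 days, i.e. SD of at least 2.5/0.468 = 5.34.

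**Step 5: how often?** Simulated beta-binomial completion on 0 to 21 days, 20 participants, 40,000 trials per setting. A split verdict means that one test is significant and the other is not, or that both are significant in opposite directions. For true means of 10 to 15 days:
- SD 4–5: about 94–100% of trials
- SD 6.34: 73–92%
- SD 8: 48–74%

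Outside that range splits are less common: at true means of 7 or 18 days they stay below half for SD 4 to 6.34.

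**Step 6: non-significance when completion is lower.** Probability that the test against 15 days is non-significant (noncentral t, 19 degrees of freedom):

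| True completion | SD 4 | SD 5 | SD 6.34 |
|---|---|---|---|
| 13 of 21 days (61.9%) | 0.44 | 0.60 | 0.73 |
| 12 of 21 days (57.1%) | 0.11 | 0.28 | 0.48 |

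**The case against.** The best defence is that nothing has been miscalculated. H3 compares with previous web-based interventions, so 10 days and 71.43% may be one result of an earlier 14-day programme in absolute and relative form. The two tests would then ask different questions (as many days, and as large a share of days), and more days with a lower share would be informative rather than contradictory. That reading is plausible and cannot be excluded. It does not remove the gap: the text does not state it, and it still does not say which answer decides H3.

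Several stronger readings are tempting but not supported:
- **That 71.43% is wrong, or that 15 of 21 days was meant.** A matched pair on 21 days could equally be 10 days with 47.6%. The documents do not show which was intended.
- **That the tests must always conflict.** An observed mean exactly on one benchmark differs significantly from the other whenever the SD is below 5/0.468 = 10.7 days, which covers almost any spread on this scale. That is a statement about an observed mean, not about the chance of a split when true completion equals a benchmark. Participants who stop using the app early could widen the spread, and the split rate falls as the SD rises.
- **That no definition exists.** Outcomes are deferred to the registry, and a figure is missing from the text provided.
- **That the plan promises to call a non-significant result similar.** It never says so; it also lists descriptive statistics and reports confidence intervals. But it offers no other route from the test to the hypothesis.

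It can also be said that this is a pilot and that significance tests are exploratory. Section 20a attaches that caveat to Aim 4, and H3 belongs to Aim 3. It is true that no progression rule in the text depends on H3, and that readers could compare the reported interval with any benchmark.

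**Conclusion.** The point holds as a gap in the decision rule for H3. The mismatch between a 14-day pair of benchmarks and a 21-day programme, and the absence of a rule for a split result, follow from the documents alone. The split rates do not: they depend on the assumed SD, on a t-interval where 20a names multilevel models, and on all 21 days being the denominator. If the denominator varies between participants, count and percent are no longer one rescaled variable and the rates would change. Within those assumptions a split is the likely outcome for true completion between the two benchmarks, apart from SDs near 8, where it is roughly an even chance for means midway between them.

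The similarity problem stands separately: a non-significant difference with 20 participants is weak evidence of similarity whichever benchmark is chosen.

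The consequence is confined to how H3 is concluded. It should be settled before the completion data are analysed.

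**What to change.** In section 20a:

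1. State the source and the programme length behind each of the two figures.
2. Define the denominator of the percent of days completed.
3. Name one benchmark, on one scale, that decides H3. Because H3 speaks of completion rates, the percent of the 21 days offered is the natural scale, and 71.43% would then be 15 days; the authors should confirm that this is what they intend. Keep 10 days only as a labelled descriptive comparator.
4. Report the estimate with its 95% confidence interval, and do not read a non-significant difference as similarity. Claim comparability only if the interval lies within a margin that the authors set and justify in advance; otherwise report completion descriptively.

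The cost is a few sentences and, if comparability is to be claimed, one justified margin. No new data are needed. The downside is that H3 may be inconclusive: at n = 20 the half-width is 1.87/21 = 8.9, 2.34/21 = 11.1 or 2.97/21 = 14.1 percentage points (SD 4, 5, 6.34). A mean exactly on 71.43% would have a lower limit of 62.5%, 60.3% or 57.3%, so a margin tighter than the half-width could not be met even there.
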